5.1.3.1 Treatment Compliance

All doses of IgPro20 will be administered by qualified personnel at the study site or at home by a home health nurse. All doses of IgPro10 will be administered by qualified personnel at the study site. Details of all infusions will be recorded. The number of unused, partially used, and empty vials will be recorded and kept until the drug accountability documentation has

been checked by the monitor. Treatment compliance will be monitored by counting the used vials, the results of which will be recorded. Treatment compliance for IgPro20 and IgPro10 will be measured as a percentage ($= 100 * [\text{used vials divided by planned vials}]$) overall and summarized using descriptive statistics. A percentage between 80% and 120% is regarded as compliant to treatment.

5.1.3.2 Overdose

Overdose is defined as the accidental or intentional infusion of any dose of a product that is considered excessive of the dose specified in the protocol. The effects of any potential overdose with IgPro20 or IgPro10 have not been studied. IgPro20 and IgPro10 are normal human proteins with broad range of normal concentrations in serum. The risk of overdosing with IgPro20 or IgPro10 is considered to be negligible. See [Section 9.6.5](#) for overdose reporting requirements.

5.1.4 Medical Devices

The Crono Infusion Pump Model S-PID 100 is an ambulatory syringe infusion pump (Cane S.R.L., Turin, Italy) that is being provided for use in this study for the purposes of administration of IgPro20. See the Crono S-PID 100 User Guide for further details of the device including proper use and training.

Medical device incidents, including those resulting from malfunctions of the device, must be detected, documented, and reported by the investigator throughout the study.

5.2 Packaging, Labeling, Supply and Storage

5.2.1 Packaging and Labeling

IgPro20 and IgPro10 will be packaged and labeled according to current ICH GMP and GCP guidelines, and national legal requirements.

Specific details regarding packaging of IgPro20 and IgPro10 are provided in the Site IP Manual. IgPro20 and IgPro10 will be labeled as required per country requirements.

5.2.2 Supply and Storage

IgPro20 and IgPro10 will be supplied to the study sites by CSLB or delegate.

IgPro20 and IgPro10 must be stored under temperature-controlled and monitored conditions at the predefined temperature range, and protected from light, in a secure storage area as specified in the Site IP Manual.

5.2.3 Dispensing Investigational Product to Subjects During Emergencies

If required to as a response to a state of emergency or public health crisis, IP may be dispensed from the study site to the subject and will be delivered in accordance with all applicable local regulations.

5.3 Accountability and Destruction

IgPro20 and IgPro10 must be used only as directed in this clinical study protocol.

The investigator or study site personnel delegated by the investigator will confirm receipt of all shipments of IP in the interactive response technology (IRT) system.

All supplies of IgPro20 and IgPro10 must be accounted for throughout the study.

Records for the delivery of IgPro20 and IgPro10 to the study site, the inventory at the study site, the use by each subject, and the destruction or return of IgPro20 and IgPro10 to CSLB / designee must be maintained by the investigator (or delegate) using the appropriate form or IRT system.

The investigator (or delegate) must provide reasons for any discrepancies in drug accountability.

Further details regarding accountability and destruction of IgPro20 and IgPro10 are provided in the Site IP Manual.

5.4 Access to Investigational Product After the End of Study

Subjects will not be provided with IP by CSLB after completion or discontinuation from the study.

6 Allocation to Treatment

6.1 Subject Assignment

After providing written informed consent, the subject will be issued with a study-level unique subject identification (ID) number via the IRT system. The subject identification number will be used to identify the subject for the duration of the study. Subject identification numbers will not be reassigned or reused.

6.2 Randomization Procedures

Eligible subjects will be randomized in a 1:1 ratio by means of IRT to either one of the following sequences: IgPro20 followed by IgPro10 (Sequence A) or IgPro10 followed by IgPro20 (Sequence B).

The randomization list will be generated by the IRT external service provider according to the approved randomization specifications. The IRT external service provider will keep the randomization code on file.

6.3 Blinding Procedures

Not applicable.

7 Contraindications, Permitted Therapies and Prohibited Therapies

7.1 Contraindications and Precautions to Further Dosing

Hypersensitivity and anaphylactic reactions: True hypersensitivity reactions are rare. They can occur in the very rare cases of IgA deficiency with anti-IgA antibodies.

Rarely, human normal immunoglobulin can induce a fall in blood pressure with an anaphylactic reaction, even in subjects who have tolerated previous treatment with human immunoglobulin.

In case of an adverse reaction, either the rate of administration must be reduced or the infusion stopped. The treatment required depends on the nature and severity of the reaction. In case of shock, standard medical treatment for shock should be implemented.

Thrombotic events: Thrombotic events can occur in treatment with IgPro20 and IgPro10. Subjects should be informed about the first symptoms of thrombotic events, including shortness of breath, pain and swelling of a limb, focal neurological deficits, and chest pain and should be advised to contact their physician immediately upon onset of symptoms. Subjects should be sufficiently hydrated before the use of IgPro20 and IgPro10 and TEE safety assessments will be performed at every site study visit as described in [Section 8.1.1.3](#).

Aseptic meningitis syndrome: AMS can occur with IgPro20 and IgPro10. The syndrome usually begins within several hours to 2 days following treatment. AMS is characterized by the following signs and symptoms: severe headache, neck stiffness, drowsiness, fever, photophobia, nausea, and vomiting. Subjects exhibiting signs and symptoms of AMS should

receive a thorough neurological examination, including cerebral spinal fluid studies, to rule out other causes of meningitis. Discontinuation of immunoglobulin treatment may result in remission of AMS within several days without sequelae.

Hemolysis: Cases of clinically significant hemolysis are rare but can appear during treatment with IgPro10. If a subject has a confirmed hemolysis of Grade 3, no further IgG should be infused and the subject should be removed from the study.

Transfusion-related acute lung injury: Noncardiogenic pulmonary edema may very rarely occur following treatment with IVIG products. Transfusion-related acute lung injury is characterized by severe respiratory distress, pulmonary edema, hypoxemia, normal left ventricular function, and fever. Symptoms typically appear within 1 to 6 hours following treatment.

Monitor patients for pulmonary adverse reactions. Transfusion-related acute lung injury may be managed using oxygen therapy with adequate ventilatory support.

Premedication: Premedication according to local standards may precede the IVIG application.

Hydration: In all subjects, hydration status should be assessed before initiation of the IVIG infusion.

Vaccination: Immunoglobulin administration may impair the efficacy of live attenuated virus vaccines such as measles, mumps, rubella, and varicella for a period of at least 6 weeks and up to 3 months. After administration of this product, an interval of 3 months should elapse before vaccination with live attenuated virus vaccines. In the case of measles, this impairment may persist for up to 1 year. Therefore, subjects receiving measles vaccines should have their antibody status checked before treatment.

7.2 Permitted Therapies

Prednisone or equivalent to ≤ 7.5 mg/day, mycophenolate (≤ 3 g/day), methotrexate (≤ 25 mg/week), azathioprine (≤ 3 mg/kg/day), hydroxychloroquine (≤ 400 mg/day; stable dose 1 month before screening) are permitted during the study. There can be no change in these permitted concomitant therapies during the study; however, temporary adjustment to permitted stable treatment during the study (eg. immunosuppressant dose interruption during infection or acute treatment with prednisone for systemic reaction / allergy) will be allowed.

7.3 Prohibited Therapies

Excluded Previous and Concomitant Therapy

The following medications / therapy are prohibited:

- Within 1 month or 5 times the half-life, whichever is longer:
 - Tocilizumab
 - Tumor necrosis factor- α inhibitors
 - Abatacept
 - Any other non-topical immunosuppressive or immunomodulatory medications
- Within 3 months or 5 times the half-life, whichever is longer:
 - Plasma exchange, blood, or IgG
 - Cyclophosphamide
- Within 6 months before screening:
 - Rituximab

7.4 Reproductive Restrictions

To be eligible for study participation, female subjects should be either:

- Post-menopausal (24 consecutive months of spontaneous amenorrhea and age \geq 51)
- Surgically sterile (having undergone one of the following surgical procedures: hysterectomy, bilateral tubal ligation, bilateral oophorectomy or bilateral salpingectomy) and at least 3 months post-sterilization
- Females with a negative serum pregnancy test at screening and negative urine pregnancy test on Week 1 before dosing

Female subjects of childbearing potential or male subjects must use a medically reliable form of contraception for the study duration and for 30 days after the last infusion of IP.

Acceptable methods of contraception are:

- Abstinence, where abstinence is the preferred and usual lifestyle of the subject, including refraining from heterosexual intercourse during the entire period of risk associated with the IP

- Hormonal methods associated with inhibition of ovulation. Acceptable hormonal methods include: oral contraceptives, contraceptive medication patch, contraceptive medication injection, estrogen / progestin vaginal ring, or contraceptive medication implant
- At least 2 barrier methods. For example, female or male condoms with spermicidal foam or spermicidal jelly, or diaphragm with spermicidal foam or spermicidal jelly. The female condom and male condom should not be used together
- Use of intrauterine device (placed more than 3 months before providing informed consent)
- Bilateral tubal occlusion of female subjects (3 months before providing informed consent)
- Vasectomy of male subjects (3 months before providing informed consent)

Periodic abstinence (calendar, symptothermal, postovulation methods), withdrawal (coitus interruptus), spermicides only, and lactational amenorrhoea method are **NOT** acceptable definitions of contraception.

8 Study Procedures and Visit Schedule

8.1 Clinical Procedures

The timing and frequency of the clinical procedures described in the following sections are detailed in the [Schedule of Assessments](#). More frequent evaluations may be performed, if clinically indicated, at the discretion of the investigator. Refer to the provided study manuals for detailed instructions on how the assessments should be performed.

All assessments and procedures are to be performed by an investigator or a qualified designee who has been trained on the study protocol.

8.1.1 Demographics, Baseline, and Safety Assessments

Demographic information such as age, sex, ethnicity / race will be collected as allowed by local law.

Medical history will include specific questions on SSc (date of diagnosis, date of first Raynaud's phenomena, date of the first non-Raynaud and its description). The history of co-morbid autoimmune disorders will be collected. Medical history will also include tobacco use. Additionally, specific cardiopulmonary, renal, and TEE risk history will be obtained.

The clinical procedures to be conducted during this study-related to the evaluation of safety are provided in Table 1. Clinical laboratory assessments are to be performed at time points as detailed in the [Schedule of Assessments](#). The time windows for each type of assessment are detailed in [Table 2](#).

Table 1 **Baseline and Safety Assessments**

Assessment	Description		
Physical examination	Full: an evaluation of the following body systems: general appearance, hydration status, skin, eyes / ears / nose / throat, spine / neck / thyroid, musculoskeletal, cardiovascular, pulmonary, abdomen, and neurological	Abbreviated: a review of the following body systems: hydration status, skin, cardiovascular, respiratory, and abdomen	
ECG	Heart Rate	PR Interval	
	QT Interval	QTcB Interval	
	QRS Duration	QTcF Interval	
	Interpretation (investigator's overall interpretation)		
Vital signs	BP (Systolic and Diastolic) in mmHg		
	Respiratory rate (breaths / minute)		
	Pulse rate (beats per minute)		
	Body temperature (Celsius)		
Pregnancy test	Urine or serum test for β -hCG, as indicated for women of childbearing potential		
	Document contraception method		
Hematology laboratory tests	Hb	Hct	Reticulocytes
	DAT	Platelets	RBC: MCV; MCH;
	ESR	Erythrocytes (RBC	MCHC; RDW
	Leukocytes with differential counts	Count) with all indices	ABO blood group
	(neutrophil, basophils, eosinophils, lymphocytes, monocytes)	IgA	including Rh factor
		Spherocytes	
		d-dimers ^a	

Assessment	Description
Serum chemistry laboratory tests	Bicarbonate Urate (Uric Acid) Glucose LDH ALT AST eGFR Haptoglobin
	Potassium Phosphate Albumin ALP Bilirubin (total, direct and indirect) GGT Creatinine
	Sodium Chloride Calcium BUN CRP CK Aldolase Protein (total)
Urine clinical laboratory tests	Total urinalysis including microscopic examination of the urine sediment.
Virology clinical laboratory tests	Blood samples are to be tested for the presence of antibodies to human immunodeficiency virus, hepatitis B, and hepatitis C.
Hemolysis safety assessment	Hematology, serum chemistry, urine for hemolysis testing, physical examination; see Section 8.1.1.2 for details
TEE safety assessments	TEE risk assessment; see Section 8.1.1.3 for details
Renal function assessments	Serum chemistry (creatinine, BUN, eGFR) and urine testing (albumin / creatinine ratio); see Section 8.1.1.4 for details
PFTs	Spirometry including CCI, CCI
Patient diary	Review or dispense new diary
AEs	Evaluation of all AEs (eg, causality / relatedness, severity, outcome, seriousness) Evaluation of AEs categorized as ISRs

ABO = Histo-blood group ABO system transferase; AE = adverse event; ALP = alkaline phosphatase; ALT = alanine aminotransferase; AST = aspartate aminotransferase; β -hCG = beta-human chorionic gonadotropin; BP = blood pressure; BUN = blood urea nitrogen; CK = creatine kinase; CRP = C-reactive protein; DAT = direct antiglobin test; CCI = CCI; ECG = electrocardiogram; eGFR = estimated glomerular filtration rate; ESR = erythrocyte sedimentation rate; CCI = CCI; GGT = gamma-glutamyl transferase; Hb = hemoglobin; Hct = hematocrit; IgA = immunoglobulin A; ISR = infusion site reaction; LDH = lactate dehydrogenase; MCH = mean corpuscular hemoglobin; MCHC = mean corpuscular hemoglobin concentration; MCV = mean corpuscular volume; PFT = pulmonary function test; RBC = red blood cell; RDW = red blood cell distribution width; Rh = rhesus; TEE = thromboembolic event

^a Will be performed only if TEE risk is high or TEE suspected

8.1.1.1 Physical Examination

A full physical exam will be conducted at Screening, Weeks 1 and 17, and EOT / Early Termination by a qualified individual, licensed in their respective state or region (eg, physician, physician's assistant, or nurse practitioner).

Full physical examination will include an evaluation of the following body systems: general appearance, hydration status, skin, eyes / ears / nose /throat, spine / neck / thyroid, musculoskeletal, cardiovascular, pulmonary, abdomen, and neurological. Abbreviated physical examination, performed at time points as detailed in the [Schedule of Assessments](#), will be composed of a review of the following body systems: hydration status, skin, cardiovascular, respiratory, and abdomen.

Any unfavorable findings considered by the investigator to be clinically significant at screening will be documented in the medical history of the subject. Unfavorable changes occurring thereafter will be documented as an AE.

8.1.1.2 Hemolysis Safety Assessment

Clinical hemolysis will be assessed at time points as detailed in the [Schedule of Assessments](#). The time windows for each assessment are detailed in [Table 2](#).

Criterion A

- Drop in hemoglobin of > 1 g/dL within a 28-day interval since the time of last administration of IgPro10 without clinical evidence of blood loss from gastrointestinal bleeding, menorrhagia, hemoptysis, major hematoma, or injury and not explained by repeated phlebotomy.

Criterion B

Presence of minor criteria documented within 28 days of last exposure to IgPro10, consisting of:

- Direct antiglobulin test (DAT) positive
- Haptoglobin $<$ lower limit of normal
- Lactate dehydrogenase $>$ upper limit of normal
- Total or indirect (unconjugated) bilirubin $>$ upper limit of normal or jaundiced
- Hemoglobinuria or red / dark urine
- Hemoglobinemia
- Spherocytosis
- Hepatosplenomegaly

Subjects fulfilling criterion A and at least 2 of the minor criteria of criterion B, where 1 of the minor criteria must be DAT positive, will be considered to have hemolysis.

If an AE of hemolysis is reported it should be graded by the investigator using this scale:

- Grade 1 – Laboratory evidence of hemolysis only (eg, direct antiglobulin test, schistocytes, decreased haptoglobin)
- Grade 2 – Clinical evidence of hemolysis and ≥ 2 g/dL decrease in hemoglobin
- Grade 3 – Transfusion or medical intervention indicated (eg, steroids)
- Grade 4 – Life-threatening consequences; urgent intervention indicated
- Grade 5 – Death

Subjects with hemolysis Grade 3 and above will be assessed by an investigator or medically qualified designee whether it is in the best interest of the subject to continue the study and safe to continue the investigational treatment.

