3.7 Stopping Criteria

No specific study stopping rules will be implemented.

A subject may withdraw from the study at any time point for any reason at their own request or at the discretion of the investigator or CSLB. Specific stopping criteria for a subject to discontinue study treatment are described in detail in [Section 4.3.1](#). If IP is discontinued, regardless of the reason, the End of Treatment (EOT) / Early Termination evaluations will be performed as completely as possible.

4 Selection and Withdrawal of Subjects

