4.3 Discontinuation of Treatment and / or Subject Withdrawal

4.3.1 Discontinuation of Study Treatment

Subjects may discontinue treatment with the IP at any time at their own request, or at the discretion of the investigator or CSLB for safety, behavioral, or administrative reasons (eg, due to an AE, protocol deviation, loss to follow-up, subject noncompliance, study termination).

Infusions will be stopped and treatment with IP will be discontinued if the subject:

- Develops anaphylaxis.

- Develops any severe or Grade 3 infusion-related reactions such as, but not limited to, TEEs (see [Section 8.1.1.3](#)), acute lung injury / pulmonary edema, acute renal injury (see [Section 8.1.1.4](#)), or Grade 3 or higher hemolysis (see [Section 8.1.1.2](#)).

Subjects will discontinue treatment with IP at the discretion of the Investigator when the reaction(s) is / are not rapidly responsive to symptomatic medication and / or brief interruption of infusion, or if symptoms recur following initial improvement or upon re-initiating infusion.

Subjects who discontinue treatment with IgPro20 or IgPro10 will be withdrawn from the study. Refer to Section 4.3.2 for details on handling subject withdrawals.

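### Protocol 8.1.1.2 leaves treatment after Grade 3 or higher hemolysis to investigator judgment, while 4.3.1 and 7.1 say to stop

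*Protocol*

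**What the plan says.** Three sections of the protocol deal with severe hemolysis.

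- **4.3.1** opens its list of mandatory stops with "Infusions will be stopped and treatment with IP will be discontinued if the subject" and then names the events. One item begins "Develops any severe or Grade 3 infusion-related reactions such as, but not limited to, TEEs" and ends "or Grade 3 or higher hemolysis", with a cross-reference to 8.1.1.2. The section closes with "Subjects who discontinue treatment with IgPro20 or IgPro10 will be withdrawn from the study".
- **7.1** covers "confirmed hemolysis of Grade 3, no further IgG should be infused and the subject should be removed from the study".
- **8.1.1.2** defines hemolysis and gives a five-point grading scale. Grade 3 means that transfusion or medical intervention is indicated; Grade 4 is "Life-threatening consequences; urgent intervention indicated". Its last sentence then sends subjects at Grade 3 and above to an investigator or medically qualified designee, who decides "whether it is in the best interest of the subject to continue the study and safe to continue the investigational treatment".

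Section 3.7 sets no study-level stopping rules. For individual subjects it says "Specific stopping criteria for a subject to discontinue study treatment are described in detail in" Section 4.3.1.

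**The concern.** The same event carries different instructions depending on which page a site opens. Section 8.1.1.2 is where staff go to grade a hemolysis event, and its sentence is the one that departs from the mandatory stop. A site acting on it in good faith could give more IgG to a subject whom 4.3.1 requires to stop. Because 3.7 has no study-level rule, protection here rests on the subject-level rule being unambiguous. What is at stake is subject safety and consistent conduct across sites. The statistical analysis is not affected.

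**Working it through.** The plan gives no figure on this point, so the check is a comparison of texts.

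| Section | Trigger | Treatment | Study status |
|---|---|---|---|
| 4.3.1 | Grade 3 or higher hemolysis, within a list of severe or Grade 3 infusion-related reactions | Must stop | Withdrawn |
| 7.1 | Confirmed Grade 3 | Should receive no more IgG | Should be removed |
| 8.1.1.2 | Grade 3 and above | Investigator or designee decides | Investigator or designee decides |

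**Does other text reconcile the three?**

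1. *The discretion paragraph in 4.3.1.* It covers reactions that respond slowly or come back. It stands apart from the mandatory list, does not mention hemolysis, and does not make the listed stops optional.
2. *The pointer in 3.7.* It names 4.3.1 as the home of the subject stopping criteria, which is good evidence that 4.3.1 is meant to govern. No sentence gives it precedence over 8.1.1.2.
3. *The cross-reference from 4.3.1 to 8.1.1.2.* Its natural purpose is to send the reader to the grading scale, which appears only there. It need not be read as handing the decision back. It does, however, lead the reader to the section with the contrary sentence.
4. *The infusion-related qualifier in 4.3.1.* It applies to hemolysis as much as to TEEs, since both sit in one list. A hemolysis event not regarded as infusion-related may fall outside 4.3.1. At confirmed Grade 3 it would still be caught by 7.1. At Grade 4 the literal wording of 7.1 does not reach it, which is a reason to extend 7.1.
5. *The SAP.* It contains no rule on the matter.

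None of these removes the conflict for confirmed Grade 3, or for infusion-related hemolysis of Grade 3 or higher.

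**How much time is there to intervene?** Under the IgPro10 schedule notes, hemolysis samples are taken 7 to 14 days after each IgPro10 dose, and cycles are 28 days apart.

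- Counted from the first infusion day: 28 − 14 = 14 to 28 − 7 = 21 days before the next cycle.
- Counted from the last of five infusion days, four days later: 28 − 4 − 14 = 10 to 28 − 4 − 7 = 17 days.

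The overall range is 10 to 21 days, before visit windows of ±2 days. Hemolysis is an adverse event of special interest (9.1.3) and must reach the sponsor within 24 hours (9.6.4). For an event found at a scheduled sample, the sponsor would therefore usually know before the next IgPro10 cycle. The margin is shorter for an event recognized between the daily infusions of one cycle or during twice-weekly IgPro20.

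**The parallel point on thromboembolism.** After confirmed DVT or PE, 8.1.1.3 says that treatment should stop but lets the subject stay for other assessments. The closing sentence of 4.3.1 withdraws every subject who stops. Both sections agree on stopping treatment where both apply; they differ on study status. The effect is on the SAP 11.2 count of special-interest events leading to study withdrawal and on routine collection of new adverse events. Serious events are still followed to resolution or stabilization (9.5).

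**The case against.** The strongest reply is that the protocol, read as a whole, points to stopping. Section 3.7 sends the reader to 4.3.1, 4.3.1 is mandatory, and 7.1 is the section on precautions to further dosing. The sentence in 8.1.1.2 orders an assessment and does not say in terms that dosing may go on. Its range also takes in Grade 5, which is death, so it looks like loose drafting. For harm to follow, an investigator would have to judge re-dosing safe in a subject who needed transfusion or other intervention, against two other sections, and the sponsor would have to let it pass after being told within 24 hours. Section 4.3.1 lets the sponsor stop treatment for safety, 4.3.2 puts the subject's interests first, and 13.3 requires documented approval for deviations.

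Most of this stands, and it lowers the importance of the point. It does not remove the contradiction. An assessment with only one permitted answer would have no purpose, so the sentence does leave continuation open. A site that follows 8.1.1.2 would not see itself as deviating, so 13.3 may not come into play. The other safeguards work by overriding what 8.1.1.2 told the site.

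A reader might infer that the protocol deliberately permits re-dosing after life-threatening hemolysis. The documents do not support that: two sections say otherwise, and exclusion criterion 25 keeps out anyone with a history of hemolysis after IVIG.

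**Conclusion.** The concern holds as an internal contradiction in a subject-level safety stopping rule. For confirmed Grade 3, or infusion-related hemolysis of Grade 3 or higher, 8.1.1.2 leaves open an outcome that 4.3.1, 7.1 or both rule out. Section 3.7 makes 4.3.1 the likelier governing text, but precedence is nowhere stated.

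Its size cannot be put as a number. The documents give no hemolysis rate, and 7.1 calls clinically significant cases rare. With 24-hour reporting in place, actual re-dosing is unlikely. The point is worth correcting but ranks below a fault that must be fixed before the plan can be used.

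Two stronger readings should be resisted. One is to count every remaining dose as excess exposure; that assumes full continued dosing after a severe event, which nothing in the documents suggests would happen. The other is to add pregnancy as a further conflict with the withdrawal sentence in 4.3.1. Section 9.6.6 does mention continuing other procedures, but it then discontinues participation during the active treatment period, so no exception is needed. The DVT/PE mismatch is real but minor, since it concerns study status only.

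**What to change.** 1. In 8.1.1.2, replace the last sentence with mandatory permanent discontinuation of investigational product at confirmed hemolysis Grade 3 or higher, referring to 4.3.1.
2. In 7.1, change the hemolysis trigger from Grade 3 to Grade 3 or higher.
3. Minor: reconcile the withdrawal sentence in 4.3.1 with 8.1.1.3, for example by excepting subjects with confirmed DVT or PE who stay for assessments off treatment.

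The cost is a wording amendment to three sections and a notice to sites. It needs no extra subjects, visits or procedures and no SAP change. The hemolysis edits bring the other two sections into line with the stopping rule already written in 4.3.1.
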